The primary outcome of this study is the percent of time spent in AF over the monitoring period (AF burden) at the 6-month time point. Secondary outcomes include total duration of AF over the 2-week monitoring period, longest daily duration of AF, measures of HRV and serum cytokine levels. Outcomes will be compared between groups using a Generalized Estimating Equations modeling approach, with 3 time points (baseline, 3 months, 6 months) and 4 terms included in the model (group effect, time effect, group by time interaction, adjustment for baseline measure).

Significant interactions will be followed by time trend analyses stratified by intervention group. If the interaction is not significant, the interaction term will be dropped from the model and the between-group comparisons will be made by combining the 3-month and 6-month data. For all pair-wise testing, we will adjust for multiple comparisons using Tukey's method. The modeling assumptions will be evaluated by plotting the residuals by the predicted values (for the constant variance assumption) and comparing the normal QQ plot with the QQ plot of the residuals (for the normality assumption). If the modeling assumptions are not satisfied, we will perform a natural log transformation of the data, to better satisfy these assumptions. For 0 values, a value of 0.01 will be added to each measure before applying the natural log. Analyses will be based on the intention-to-treat principle. In post-hoc exploratory analyses, we will use logistic regression analysis to identify predictors of clinical and cytokine response to LLTS, defined as a decrease of AF burden and a decrease in cytokines at 6-month follow-up, respectively. Those variables that which are associated with response to LLTS in univariate analysis at p<0.1 will be entered into a multivariate logistic regression model, using a backward elimination method to identify the most parsimonious model. In light of the limited sample size, such analyses will be underpowered and will be considered hypothesis-generating only. Statistical significance will be declared at p<0.05.

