Sample size and power calculations: For purposes of sample size calculations we have simplified the analysis to focus on the AF burden at the 6-month time point between the 2 groups. Assuming a mean±standard deviation AF burden in the control group of $28.4\pm31.2\%$ ³⁴ and a 87% reduction in the LLTS group to 3.7% (assuming a common standard deviation of 31.2%), 26 patients per group would provide 80% power to detect the specified effect sizes at a two-sided significance α level of 0.05. Approximately 30 patients with paroxysmal AF are seen in our clinics each month. Assuming that 1 out of 4 eligible patients would agree to participate in the study, we should be able to enroll the required number of patients within the proposed 17 months, allowing for 6 months of additional follow up and a final month for data analysis.

F. Gender/Minority/Pediatric Inclusion for Research

Participants will be age 21 or older. Race, minority status and gender will not affect enrollment.

[figure not shown]
G. Human participants

The study population will include 52 male/female patients with paroxysmal AF, aged 21 or older, including all races. Since AF is extremely rare in patients less than 21 years old, this age limit is not expected to affect the overall results.

Inclusion Criteria:

- 1. Male and female patients older than 21 year old
- 2. Paroxysmal AF

Exclusion Criteria:

- 1. Left ventricular dysfunction (Left ventricular ejection fraction <40%)
- 2. Significant valvular disorder (i.e., prosthetic valve or hemodynamically relevant valvular diseases)
- 3. Recent (<6 months) stroke or myocardial infarction
- 4. Severe heart failure (NYHA IV)
- 5. Left atrial dilatation (>55mm)
- 6. Recurrent vaso-vagal syncopal episodes
- 7. Unilateral or bilateral vagotomy
- 8. Pregnancy or breast feeding
- 9. Sick sinus syndrome, 2nd or 3rd degree AV block, bifascicular block or prolonged (PR>300ms) 1st degree AV block.
- 2. Identify sources of research material in the form of specimens, records or data.

The research information will consist of the AF burden and serum inflammatory cytokines at each time point specified in the protocol (see Figure 4).

- 3. Describe plans for recruitment and consent procedures to be followed.
- a. Describe the location where consent is most likely to take place (will consent be obtained while an inpatient, in the ER/ICU, will consents be mailed with follow-up meeting to discuss the consent, etc.).

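### The between-arm difference in AF burden at 6 months is named and powered as primary, but an interaction pre-test sends the analysis to within-arm trends or a pooled 3- and 6-month contrast instead

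*Combined protocol and SAP*

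**What the plan says.** All of this is in section E (Statistical methods) of the combined protocol and SAP.

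- **Primary outcome:** "percent of time spent in AF over the monitoring period (AF burden) at the 6-month time point".
- **Power basis:** under the sample size heading, "we have simplified the analysis to focus on the AF burden at the 6-month time point between the 2 groups". The inputs are a control mean of 28.4% (SD 31.2%), 3.7% in the active arm with the same SD, and 26 patients per group for 80% power at two-sided 0.05.
- **Model:** generalized estimating equations "with 3 time points (baseline, 3 months, 6 months) and 4 terms included in the model". The terms are group, time, and "group by time interaction, adjustment for baseline measure".
- **If the interaction is significant:** "Significant interactions will be followed by time trend analyses stratified by intervention group".
- **If it is not:** the term is taken out, after which "the between-group comparisons will be made by combining the 3-month and 6-month data".
- **Pair-wise tests:** "For all pair-wise testing, we will adjust for multiple comparisons" by Tukey's method. The pairs are not listed.

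No sentence says which p-value decides the trial, and no separate significance level is given for the interaction test.

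**The concern.** Neither branch is the contrast that the trial names and powers. A significant interaction is evidence of a difference between arms, but it does not estimate the difference at 6 months. The follow-up the plan states for it is an analysis within each arm, which sets aside the randomised comparison with sham. A non-significant interaction leads to an average over 3 and 6 months. That equals the 6-month difference only if the effect is the same at both visits.

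The role of baseline is also unclear. It is listed both as one of three outcome time points and as the adjustment term. If the interaction spans baseline, a working device itself creates the interaction, because the arms are alike at baseline and differ later. If it spans only 3 and 6 months, a constant effect creates none. Two analysts following the same text could report different primary results.

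At stake are the meaning of the primary estimate, the relevance of the stated power and, depending on how success is read, the 5% error rate. A pooled contrast can also be significant when the effect has gone by 6 months.

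**Working it through.** **Inputs from the plan.** Difference 28.4 − 3.7 = 24.7 points; common SD 31.2; 26 per arm; two-sided 0.05.

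**Assumptions not in the plan.** Equal within-patient correlation r = 0.3, 0.5, 0.7; normal data; no missing visits; the effect at 3 months as stated in each step. Exact tests stand in for GEE. Results come from 20,000 to 40,000 simulated trials per scenario. Triplets below are for r = 0.3 / 0.5 / 0.7.

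**Step 1. The plan's own figure.** The noncentrality is 24.7 / (31.2 × √(2/26)) = 2.85 on 50 degrees of freedom. Power is 79.9% by the noncentral t (81.4% by the normal approximation). The 26 per arm reproduces, for the 6-month difference only.

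**Step 2. Baseline as an outcome time point.** The group-by-time test has 2 degrees of freedom (Hotelling T² on the changes from baseline). With 24.7 points at both 3 and 6 months, it is significant in 67.6 / 82.4 / 96.6% of trials. The plan's next step is then within-arm trends.

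**Step 3. Interaction over 3 and 6 months only, effect building up.** With 12.35 points at 3 months and 24.7 at 6, the test on the 3-to-6-month change is non-significant in 78.0 / 70.8 / 56.0% of trials. The pooled contrast then targets (12.35 + 24.7)/2 = 18.5 points; the simulated mean in those trials was 18.5–18.6.

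**Step 4. Same reading, effect that fades.** With 12.35 points at 3 months and none at 6, a non-significant interaction followed by a significant pooled contrast occurs in 12.1 / 11.7 / 12.1% of trials. A 6-month test is significant in about 5%.

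**Step 5. Same reading, constant effect.** About 95% of trials reach the pooled contrast. It estimates the same 24.7 points with power 95.8 / 97.5 / 99.6%, against 83 / 89 / 97% for the baseline-adjusted 6-month test. Here the rule does no harm.

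**Step 6. No true effect.** The chance that either the interaction or the pooled contrast is significant:

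| Interaction covers | Pooled contrast | Type I error |
|---|---|---|
| Baseline, 3 and 6 months | Baseline-adjusted | 8.2–8.8% |
| Baseline, 3 and 6 months | Unadjusted | 9.5–9.6% |
| 3 and 6 months only | Baseline-adjusted | 9.7–9.8% |

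**Step 7. A 6-month contrast under Tukey.** The critical |t| is the 0.95 studentized range for k means and 50 degrees of freedom, divided by √2. Power without baseline adjustment uses the noncentrality from step 1.

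| Means in the family | Critical \|t\| | Power, unadjusted | Power, baseline-adjusted (r 0.3–0.7) |
|---|---|---|---|
| 2 | 2.01 | 79.9% | 83–97% |
| 4 | 2.66 | 58.1% | 62–90% |
| 6 | 2.96 | 46.4% | 51–83% |

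**Step 8. Skewed data.** With beta-distributed burden (mean 28.4, SD 31.2) and active values multiplied by 3.7/28.4, step 2 gives 70.2 / 79.5 / 90.8%, the non-significant share in step 3 is 66.8 / 57.7 / 40.7%, and step 6 gives 9.4–9.7%. The scaling shrinks the active-arm SD to 31.2 × 3.7/28.4 = 4.1, unlike the plan's common SD, so this checks the pattern rather than the design.

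**The case against.** The best defence is that the rule is loosely worded rather than wrong.

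- **The kinder reading of baseline is plausible.** Baseline is an adjustment term, and only 3- and 6-month data are pooled, so the interaction may well cover those two visits. With a constant effect the plan then does better than the 6-month test (step 5). This stands, and it makes step 2 conditional on the other reading. It does not help when the effect changes between visits.
- **A 6-month contrast is available.** The fitted interaction model contains it, the pair-wise sentence permits it, and trends may be meant to accompany it rather than replace it. True, but it is not named or made decisive, its Tukey family is open, and the pooled branch is unaffected.
- **The 8–10% error depends on a success rule the plan does not contain.** Correct. If a significant 3-versus-6-month interaction instead led to the adjusted 6-month contrast, and a non-significant one to the pooled contrast, the error would be about 6%. That is milder, though still above 5%.
- **The pooled contrast fits Aim 1,** which speaks of AF burden over six months. But section E fixes the outcome at the 6-month visit.
- **The plan admits simplifying for sample size.** That explains the power calculation. It does not reconcile the named outcome with the rule.
- **The magnitudes rest on assumed correlations and 3-month effects, on the raw scale.** They do, and the plan allows a log transformation, under which point differences would read differently. The mismatch itself needs no such assumption.

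**Conclusion.** The concern holds and should be settled before unblinding. The plan states a rule that departs from its own primary outcome, so this is more than a missing detail. That conclusion follows from the text alone.

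How much it matters depends on the reading of baseline and the course of the effect. It ranges from harmless (constant effect, interaction over 3 and 6 months) to a primary analysis that usually continues as within-arm trends when the device works (68–97% of trials, baseline as a time point). In between, it may estimate 18.5 points instead of 24.7, or give a significant pooled result in about 12% of trials with no 6-month effect. The type I error is 8–10% if either test counts as success and about 6% under the kinder routing. All these figures assume 26 complete patients per arm and r of 0.3 to 0.7. The sample size arithmetic is sound for the contrast it describes.

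**What to change.** Amend section E to state:

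1. One primary test: the between-arm difference in AF burden at 6 months from the baseline-adjusted model, two-sided 0.05, with no Tukey adjustment.
2. Baseline enters only as the covariate; the outcome time points are 3 and 6 months.
3. Group by time stays in the model whatever its p-value, and the sentence that drops it is deleted.
4. The 3-month difference, the 3- and 6-month average and the within-arm trends are secondary, and the Tukey family for any secondary pair-wise tests is named.

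The cost is a few sentences before unblinding. With complete data, 26 per arm gives 80% power unadjusted and 83–97% with baseline adjustment at the assumed correlations, so 52 patients still suffice on the plan's own inputs. The price is that the pooled contrast, which is more powerful when the effect is constant (step 5), becomes secondary.

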The overall objective of this proposal is to translate in ambulatory patients with paroxysmal AF the results of our previous studies showing acute suppression of AF and inflammation in anesthetized canines as well as humans, in order to examine the long-term therapeutic effects of this approach. We hypothesize that intermittent (1 hour daily) LLTS for 6 months may result in long-term decrease of AF burden and suppression inflammatory cytokines in patients with paroxysmal AF. Patients will be randomized to either active or sham LLTS. LLTS will be delivered through a transcutaneous vagus nerve stimulation (tVNS) device for 1 hour daily over a 6-month period. AF burden will be defined as the percent of time spent in AF over a 2-week period, assessed by noninvasive continuous ECG monitoring at baseline, 3 and at 6 months. In addition, blood samples will be collected from patients at baseline, and at 3 and 6 months, for cytokine measurement. These investigations will establish the first evidence of the long-term effects of LLTS on AF suppression in patients with paroxysmal AF and may provide the basis for a potential expansion of the therapeutic targets of this treatment modality beyond AF.

A. Specific aims

[figure not shown]
Specific Aim 1: To examine the effect of intermittent (1 hour daily) LLTS on AF burden in patients with paroxysmal AF over a 6-month period relative to sham LLTS. Patients will be randomized to either active or sham LLTS. LLTS will be delivered through a transcutaneous vagus nerve stimulation (tVNS) device for 1 hour daily over a 6-month period. LLTS will be delivered by the patients themselves at home after individual training. AF burden will be defined as the percent of time spent in AF over a 2-week period, assessed by noninvasive continuous ECG monitoring at baseline, and at 3 and 6 months.

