sinus rhythm for AF ablation, were randomized to either 1 hour of LLTS (n=20) or control (n=20). LLTS in the right ear, 50% lower than the voltage that slowed the sinus rate, was accomplished by attaching a flat metal clip onto the tragus. Under general anesthesia, AF was induced at baseline and after 1 hour of LLTS or sham stimulation and were analyzed for inflammatory cytokines, including TNF α and CRP, using a multiplex immunoassay. Pacing-induced AF duration decreased significantly by 6.3±1.9 min compared to baseline in the LLTS group, but not in the control (p=0.002 for comparison between groups; Figure 2A). AF cycle length increased significantly from baseline by 28.8±6.5ms in the LLTS group, but not in the control (p=0.0002 for comparison between groups). Systemic (femoral vein) but not coronary sinus TNF α and CRP levels decreased significantly only in the LLTS group (Figure 2B). Importantly, the magnitude of decrease in TNF- α levels by LLTS was comparable with the difference between patients with active vs. inactive inflammatory diseases ³³. We concluded that LLTS acutely suppresses AF and decreases inflammatory cytokines in patients with paroxysmal AF, supporting the emerging paradigm of

neuromodulation to treat AF ³⁰. The results of this study were published in the Journal of the American College of Cardiology ³⁰.

D. Research design and Methods

Specific Aim 1: To examine the effect of intermittent (1 hour daily) LLTS on AF burden in patients with paroxysmal AF over a 6-month period.

This is a prospective double-blind randomized controlled study. Patients with paroxysmal AF, documented by ECG, pacemaker/implantable cardioverter defibrillator (ICD) electrogram or Holter monitor, within 3 months of randomization on 2 separate occasions, at least 1 day apart, of at least 30 seconds duration, will be eligible for inclusion in the study.

Patients will be excluded if they have any of the following:

- 1. Left ventricular dysfunction (Left ventricular ejection fraction <40%)
- 2. Significant valvular disorder (i.e., prosthetic valve or hemodynamically relevant valvular diseases)
- 3. Recent (<6 months) stroke or myocardial infarction
- 4. Severe heart failure (NYHA IV)
- 5. Left atrial dilatation (>55mm)
- 6. Recurrent vaso-vagal syncopal episodes
- 7. Unilateral or bilateral vagotomy
- 8. Sick sinus syndrome, 2nd or 3rd degree AV block, bifascicular block or prolonged (PR>300ms) 1st degree AV block

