Patients will be recruited from the inpatient services and outpatient clinics of the University of Oklahoma Health Sciences Center. A meeting with all study personnel to review the study protocol will be held before initiation of the study, as well as every 3-6 months, depending on study progress. Informed consent will be obtained prior to enrollment in the study. The randomization schedule will be implemented with the use of concealed envelopes and it will be stratified by sex. Blocked randomization will be used to decrease the chance of imbalances in the two groups over time.

After informed consent and screening procedures are completed, all patients will undergo noninvasive continuous ECG monitoring for 2 weeks to evaluate their AF burden (the percent of time spent in AF) using an adhesive waterproof continuous monitoring patch (Zio[®] Patch). The Zio[®] Patch (iRhythm Technologies, Inc) is an FDA approved, single-lead, lightweight, 14-day ambulatory ECG adhesive patch monitor. The patch is well tolerated and allows significantly longer continuous monitoring than a regular Holter monitor, leading to an improved AF detection rate ³⁴. After the 2-week monitoring period, patients will be randomly assigned (1:1) to active or sham LLTS. Patients will be blinded to the treatment allocation, and every effort will be made to conceal from the study personnel the nature of the intervention in each study arm. Blinding of the patients will be accomplished by having a sham control arm, in which stimulation will be delivered to a different site (the ear lobe), devoid of vagal innervation ³⁵. By doing so, all patients will be aware that they are receiving stimulation, but they will not be told which site achieves active VN

stimulation. The patients will be requested to refrain from discussing the details of their treatment with other patients in the clinic and with the physicians, nurses and the rest of clinic staff. The clinical coordinator and a clinic physician who will not participate in any of the other study related assessments will be unblinded to the treatment allocation and will instruct the patients on the proper use of the device. These study personnel will be designated to address the patients' questions and concerns as well as to record any side effects related to the use of the device.

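### A patient with no AF on the baseline patch cannot meet the definition of clinical response, which can bias the exploratory search for predictors linked to baseline burden

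*Combined protocol and SAP*

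**What the plan says.** - **Outcome scale.** In the opening summary and Section A, "AF burden will be defined as the percent of time spent in AF over a 2-week period". The scale therefore has a floor of 0%.
- **Entry.** Section D, Specific Aim 1, asks for documented AF "within 3 months of randomization on 2 separate occasions, at least 1 day apart, of at least 30 seconds duration". The inclusion list in Section G asks only for age and "paroxysmal AF". Neither sets a minimum burden.
- **Baseline patch and randomisation.** Once consent and screening are complete, "all patients will undergo noninvasive continuous ECG monitoring for 2 weeks to evaluate their AF burden". Then, "After the 2-week monitoring period, patients will be randomly assigned (1:1) to active or sham LLTS". No condition on the patch result is given.
- **Response.** Section E sets out logistic regression for "predictors of clinical and cytokine response to LLTS, defined as a decrease of AF burden and a decrease in cytokines at 6-month follow-up". Candidates with univariate p<0.1 go forward to backward elimination. Section D, Specific Aim 2, adds exploratory work linking clinical to cytokine response and looking for predictors among baseline cytokine levels.
- **Zeros.** The only rule is for the log transformation: "For 0 values, a value of 0.01 will be added to each measure before applying the natural log".
- **Status.** Section E describes the predictor analyses as post hoc, exploratory, underpowered and hypothesis-generating.

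**The concern.** Response is a binary label that some patients cannot earn. A patient at 0% on both the baseline and the 6-month patch has the best result the outcome allows, yet receives the same code as a patient whose AF increased. The label then partly records whether AF happened to be present in the baseline fortnight. A baseline characteristic that makes an AF-free fortnight more likely, such as infrequent episodes or effective antiarrhythmic drugs (which Section D says are continued), can look like a predictor of non-response even if it has no bearing on the effect of stimulation.

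Baseline cytokines are the named candidates, and the protocol's rationale ties inflammation to AF. If cytokine levels track baseline burden, they are exposed to this artefact. The planned comparison of clinical with cytokine response uses the same label and inherits the problem.

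**Working it through.** **Does the text allow it?** Floor of 0%, plus no burden condition at entry, plus no burden condition at randomisation, means a 0% baseline can be randomised. A decrease needs a 6-month value below baseline, which is impossible from 0%. The added 0.01 does not help: 0.01 at baseline and 0.01 at 6 months is still no decrease. Section E does not name the comparator for the decrease; baseline is the only natural reading.

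**The plan's own figures.** It gives none for the responder analysis or the share of zero baselines. The numbers analysed come from the sample size paragraph. Difference 28.4 − 3.7 = 24.7, SD 31.2; a two-sided t-test at 0.05 needs 26.04 per group for 80% power, and 26 per group gives 79.9%. The plan's 26 per group, 52 in total, reproduces. The text does not say whether the predictor model uses the LLTS arm or both arms, so both n=26 and n=52 are shown.

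**Ceiling on the response rate.** Let f be the share with 0% at baseline (assumed) and r the true response rate among the rest (assumed 70%). Maximum rate = 1 − f; observed rate = r(1 − f).

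| f | zeros among 52 | maximum | observed, r = 70% |
|---|---|---|---|
| 10% | 5 | 90% | 63% |
| 20% | 10 | 80% | 56% |
| 30% | 16 | 70% | 49% |
| 40% | 21 | 60% | 42% |

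**Zero baseline as its own predictor.** No patient at zero responds. With about 70% response among the others, Fisher's exact test gives p = 0.046 for 3 zeros among 26 (16 of 23 others respond) and p = 0.004 for 5 among 52 (33 of 47).

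**False selection of a binary feature.** Simulation: feature split evenly, share of zeros differing between its two levels, 70% response among patients with baseline AF whatever the feature, Fisher's exact test at p<0.1.

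| zeros by feature level | n=26 | n=52 |
|---|---|---|
| 10% vs 50% | 25% | 59% |
| 15% vs 45% | 16% | 39% |
| 10% vs 30% | 9% | 22% |
| 5% vs 15% | 6% | 10% |

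Restricted to baseline burden above 0%, the rates are about 4–7%. They lie below 10% because the exact test is conservative at these sizes.

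**False selection of a continuous marker.** Same 70% response, two-sample t-test at p<0.1, f from 10% to 40%:

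| correlation with baseline burden | n=26 | n=52 |
|---|---|---|
| 0 | 9–10% | 10–11% |
| 0.3 | 13–23% | 15–33% |
| 0.5 | 17–38% | 24–65% |

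After restriction every cell returns to about 9–11%, the nominal level.

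**The case against.** The strongest reply is that little depends on this analysis. No primary or secondary outcome uses the response label, the primary outcome is continuous 6-month burden adjusted for baseline, and Section E already warns that the predictor work is underpowered. That stands and sets the severity. It does not remove the point: a warning about low power covers imprecision, whereas this is a systematic error that is flagged more often as n grows.

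The size can also be disputed, and several stronger readings that a reader might infer do not hold.

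- *That most baseline patches will be empty.* If episodes arrive at random at two per 91 days, the chance of none in 14 days is exp(−2 × 14/91) = 73.5%. But the entry rule counts documented episodes, and ECG or Holter samples only part of three months, so the true rate may be much higher. At 8 episodes the chance is 29%, at 15 it is 10%. The planning mean burden of 28.4% and the references to ablation patients in Section G also argue against the high end, though they do not exclude zeros.
- *That false selection is near certain.* Rates of about 64% (n=26) and 93% (n=52) for 10% versus 50% zeros arise only if about 99% of patients with baseline AF respond, which turns the planned 87% reduction in group mean into a uniform effect in every patient. Even then, selection is not automatic.
- *That the device goes untested in zero-baseline patients.* They receive six months of stimulation and can worsen; what they cannot do is show a decrease.
- *That the analysis is meant to choose whom a later trial enrols.* The protocol says only that the study's results may form the basis of a larger trial.
- *That the zero-value rule shows zero baselines are expected.* It applies to every measure, including follow-up values.

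**Conclusion.** The point holds as a low-severity flaw in the definition of clinical response. That zero-baseline patients can be randomised and can only be scored as non-responders follows from the text without any assumption. How far this distorts predictor selection rests on an assumed share of zeros, an assumed 70% response among the rest, and how strongly the candidate feature tracks baseline burden. Under those assumptions false selection runs from negligible to more than half of trials. Features unrelated to baseline burden are not biased, and the primary comparison and the sample size are untouched.

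**What to change.** Add to Section E, and apply to the analysis in Section D, Specific Aim 2, that relates clinical to cytokine response:

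- Clinical response is assessed only in patients whose baseline AF burden is above 0%.
- The number with 0% at baseline is reported by arm, and their 6-month burden is described separately and not counted as non-response.
- All randomised patients stay in the primary analysis.

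This takes a few sentences and no new data or visits, and should be fixed before unblinding. It removes about 5 to 21 of 52 patients (31 to 47 remain) if 10–40% have a zero baseline, from an analysis that is already underpowered; those patients could not have shown the response being modelled. Restriction does not deal with regression to the mean, since it selects on a positive baseline value. Modelling 6-month burden adjusted for baseline, in place of a binary label, is a reasonable alternative that keeps everyone.
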